7.5.1 Expedited reporting by investigator to Celgene

Serious adverse events (SAE) are defined above. The investigator should inform Celgene in writing using a Celgene SAE form or MEDWATCH 3500A form of any SAE within 24 hours of being aware of the event. This form must be completed and supplied to the UTMDACC IRB, UTMDACC IND Office, and Celgene within 24 hours/1 business day. The initial report must be as complete as possible, including an assessment of the causal relationship between the event and the investigational product(s) if available. Information not available at the time of the initial report (e.g., an end date for the adverse event or laboratory values received after the report) must be documented on a follow-up M.D. Anderson Cancer Center SAE form.. A final report to document resolution of the SAE is required. The M.D. Anderson Protocol number (2009-0972) and the Celgene protocol number (PO-WM-PI-0006) should be included on SAE reports to Celgene. A copy of the fax transmission confirmation of the SAE report to Celgene should be attached to the SAE and retained with the patient records.

7.5.2 Report of Adverse Events to the Institutional Review Board

The principal investigator is required to notify his/her Institutional Review Board of a serious adverse event according to institutional policy.

7.5.3 Investigator Reporting to the FDA

Adverse drug reactions that are **Serious, Unlisted/unexpected, and at least possibly associated to the drug**, and that have not previously been reported in the Investigators

brochure, or reference safety information document should be reported promptly to the Food and Drug Administration (FDA) in writing by each investigator/physician engaged in clinical research. A clear description of the suspected reaction should be provided along with an assessment as to whether the event is drug or disease related.

Serious adverse events will be forwarded to the FDA by the IND Sponsor (Safety Project Manager IND Office) according to 21 CFR 312.32.

7.6 Adverse event updates/IND safety reports

Celgene shall notify the Investigator via an IND Safety Report of the following information:

- Any AE associated with the use of study drug in this study or in other studies that is both serious and unexpected.
- Any finding from tests in laboratory animals that suggests a significant risk for human subjects including reports of mutagenicity, teratogenicity, or carcinogenicity.

The Investigator shall notify his/her IRB/EC promptly of these new serious and unexpected AE(s) or significant risks to subjects.

The Investigator must keep copies of all AE information, including correspondence with Celgene and the IRB/EC, on file (see Section 12.4 for records retention information).

8 Response Criteria²⁵

Baseline disease assessments must occur within \leq 28 days of study drug administration.

Response assessments will be performed after each cycle of pomalidomide has been administered. Response will be assessed by either the principal investigator or a sub-investigator, and then documented in the UTMDACC protocol data management system (PDMS). Because of the IgM flare phenomenon²⁶, progressive disease cannot be confirmed until the response assessment performed after the second cycle of pomalidomide, has been reviewed. All partial and complete responses must be confirmed with a second efficacy assessment, performed at least 6 weeks later.

Definitions of response:

1. **Complete response (CR):** categorized by the disappearance of serum and urine monoclonal protein determined by immunofixation, absence of malignant cells in the bone marrow determined by histologic evaluation, resolution of adenopathy/organomegaly (confirmed by computed tomography [CT] scan) and no signs or symptoms attributable to WM. Reconfirmation of the CR status is required \geq 6 weeks later with a second immunofixation.
2. **Partial response (PR):** categorized by \geq 50% reduction of serum monoclonal IgM concentration determined by protein electrophoresis, \geq 50% decrease in

adenopathy/organomegaly on physical examination or on CT scan and no new symptoms or signs of active disease.

3. **Minor response (MR):** categorized by a $\geq 25\%$ but $<50\%$ reduction of serum monoclonal IgM concentration determined by protein electrophoresis and no new symptoms or signs of active disease.
4. **Stable disease (SD):** categorized by a $<25\%$ reduction and $<25\%$ increase of serum monoclonal IgM concentration determined by protein electrophoresis, without progression of adenopathy/organomegaly, cytopenias or clinically significant symptoms caused by disease and/or signs of WM.
5. **Progressive disease (PD):** categorized by a $\geq 25\%$ increase of serum monoclonal IgM concentration determined by protein electrophoresis confirmed by a second measurement or progression of clinically significant findings caused by disease (e.g. anemia, thrombocytopenia, leukopenia or bulky adenopathy/organomegaly) or symptoms (e.g. unexplained recurrent fever $\geq 38.4^{\circ}\text{C}$, drenching night sweats, $\geq 10\%$ weight loss, hyperviscosity, neuropathy or symptomatic cryoglobulinemia) attributable to WM.

Definition of Relapse/Progression after response:

1. **Relapse from CR:** categorized by the appearance of the monoclonal protein in serum or urine, confirmed by a second determination, recurrence of bone marrow involvement by lymphoplasmacytic cells, recurrence/development of lymphadenopathies/splenomegaly or symptoms/signs attributable to WM.
2. **Progression from PR:** categorized by $\geq 25\%$ increase of serum monoclonal IgM concentration from the lowest attained response value determined by protein electrophoresis, confirmed by a second measurement or progression of clinically significant signs (anemia, thrombocytopenia, leukopenia, or bulky adenopathy/organomegaly) or symptoms (e.g. unexplained recurrent fever $\geq 38.4^{\circ}\text{C}$, drenching night sweats, $\geq 10\%$ weight loss, hyperviscosity, neuropathy, or symptomatic cryoglobulinemia) attributable to WM. An absolute increase of 5g/L (confirmed on a second determination) is required in order to define disease progression when the only criterion for progressive disease is the increase of M protein size. In a patient with a localized large mass and/or a high level of lactic dehydrogenase, at relapse or progression, a biopsy should be considered to assess the possibility that transformation to diffuse large B cell lymphoma has occurred.

9 Protocol Amendments/Deviations

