¹⁰If screening assessments were done within 7 days of Cycle 1, Day 1, they do not need to be repeated on Cycle 1, Day 1.

¹¹An additional safety assessment will be done 30 days (+/- 1 week) following the last dose of study drug.

¹²Only enough pomalidomide for 1 cycle of therapy may be provided to the patient each cycle.

¹³Serum and urine protein electrophoresis; Quantitative serum IgG, IgA, and IgM; Free serum kappa and lambda light chains; Serum and urine immunofixation studies will be performed at screening, and to evaluate for and confirm CR. Response assessment labs should be performed within 5 days prior to Day 1 of each cycle.

¹⁴All PRs and CRs must be confirmed by repeat Response Assessment labs no less than 6 weeks after the criteria for response are first met.

¹⁵Day 1 may be delayed up to 7 days to accommodate holidays/weekends/inclement weather and other unforeseen events.

¹⁶Information may be obtained without having the subject visit the study center (i.e. phone call).

¹⁷To be repeated if a complete remission is suspected

¹⁸ Chest x-ray will only be performed as part of the screening evaluation and when CR/MRI of the chest is indicated as part of the patient's restaging evaluation.

¹⁹ Assessments to be performed at Cycle 1 Days 1, 8, 15 and 22 may be performed +/- 2 business days from the planned date to accommodate holidays, inclement weather and other unforeseen events.

²⁰ Hep B -we will check Hep B surface antigen. If positive, we will check Hep B surface antibody and Hep B viral DNA. If Hep B surface antibody is negative and/or Hep B viral DNA shows circulating virus, patient will be excluded ; Hep C – we will check Hep C Antibody. If positive, we will check Hep C Viral PCR. If it shows circulating virus, patient will be excluded

²¹ Starting with Cycle 3, CT scans will be performed every 4 months for the first 2 years, every 6 months for the next 2 years, and then once a year thereafter.

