5.2.2 Secondary Endpoints

- The safety and toxicity profile of pomalidomide will be evaluated after all patients to be enrolled have completed 1 cycle of therapy; patients who received at least 1 dose of pomalidomide will be eligible for evaluation.
- The efficacy of pomalidomide will be measured by best response to therapy during. It will be assessed as the best response during each patient's course of therapy. The collective data will be summed at study completion. Patients will be considered evaluable if they have completed at least 1 cycle of therapy.

6 Investigational Plan

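### Minor response is the only improvement category that needs no confirmation, so chance variation in IgM can inflate the minor-response count

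*Combined protocol and SAP*

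**What the plan says.** Section 8 defines five categories: CR, PR, MR, stable disease (SD) and PD.

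- **CR and PR.** "All partial and complete responses must be confirmed with a second efficacy assessment, performed at least 6 weeks later". Footnotes 9 and 14 of the Section 2.0 schedule repeat this for scans and for response labs. Both name PR and CR only.
- **PD by IgM.** It requires an "increase of serum monoclonal IgM concentration determined by protein electrophoresis confirmed by a second measurement".
- **MR.** It requires a 25% to under 50% "reduction of serum monoclonal IgM concentration determined by protein electrophoresis and no new symptoms or signs of active disease". No repeat or minimum duration is stated.
- **SD.** It requires an IgM change of less than 25% in either direction, "without progression of adenopathy/organomegaly, cytopenias or clinically significant symptoms caused by disease and/or signs of WM". This is also unconfirmed.

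On timing, Section 8 says "Response assessments will be performed after each cycle of pomalidomide has been administered". Footnote 13 says "Response assessment labs should be performed within 5 days prior to Day 1 of each cycle". Footnote 9, attached to the CT/MRI row, places the first response assessment at completion of cycle 2.

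Section 5.2.2 makes efficacy a secondary endpoint: "It will be assessed as the best response during each patient's course of therapy". The data are then to be summed at study completion. No response rate is defined. Under Section 6.4.2, treatment continues until progression or unacceptable toxicity, so the number of readings per patient has no fixed limit.

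**The concern.** A best-response endpoint takes the most favourable of a patient's repeated assessments. If a category can be entered on one laboratory value, the endpoint depends on the lowest of many noisy readings, each compared with a baseline that is itself noisy. Taking the best reading can only move a patient up a category, and every further cycle adds another chance. The plan guards against this for CR, PR and IgM-based PD, but not for MR.

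What is at stake is how the efficacy table reads. Some patients whose IgM has not truly fallen by 25% would appear under MR instead of SD, and patients treated longer would have more opportunity to do so. If the MR line is read as evidence of single-agent activity, or is added to CR and PR, that evidence is partly noise.

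**Working it through.** **1. Which categories can one value establish?**

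| Category | IgM condition | Repeat required? |
|---|---|---|
| CR | Monoclonal protein gone on immunofixation (with marrow, imaging and symptom conditions) | Yes, at least 6 weeks later |
| PR | Fall of 50% or more (with adenopathy and symptom conditions) | Yes, at least 6 weeks later |
| MR | Fall of 25% to under 50%, no new symptoms or signs | No |
| SD | Change under 25% either way | No |
| PD by IgM | Rise of 25% or more | Yes, second measurement |

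SD is the no-change category, so leaving it unconfirmed does not inflate activity. MR is the only improvement category without a repeat.

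**2. The plan's own figures.** The documents state no expected response rate and no IgM variability, so there is no efficacy figure to reproduce. The one sample size given, a maximum of 30 (Sections 6.4.1 and 11.6), follows from 6 patients at Schedule A level 1 plus 4 levels × 6 on Schedule B = 30. It serves below only as the largest possible denominator.

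**3. Assumptions (not in the documents).** One baseline value; lognormal within-patient variation with CV 5%, 10% or 15%; independent errors; a constant true level t relative to baseline; K = 3, 6 or 12 follow-up readings. With 4-weekly readings, the first scheduled repeat at least 6 weeks later is two cycles on.

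**4. Formulas.**

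- σ = √ln(1 + CV²), which is 0.0500, 0.0998 and 0.1492 for the three CVs.
- Chance that one given reading is at or below 0.75 of baseline: Φ(ln(0.75/t) / (σ√2)). With t = 1 and CV 10%: ln 0.75 = −0.2877, and −0.2877 / 0.1411 = −2.04, giving 2.1%. At CV 5% it is about 0.002%; at CV 15% it is 8.6%.
- All K readings share the same baseline error z. Given z, each is low with probability p(z) = Φ(ln(0.75/t)/σ + z). The chance of at least one low reading is 1 − E[(1 − p(z))^K]. The confirmed chance is the probability, averaged over z, that some pair of readings two cycles apart are both low.

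**5. Results: one value → repeat at 6 weeks or more.**

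| True change | CV | K = 3 | K = 6 | K = 12 |
|---|---|---|---|---|
| None | 5% | <0.1% → 0% | <0.1% → 0% | <0.1% → 0% |
| None | 10% | 5.3% → 0.4% | 8.8% → 1.1% | 13.8% → 2.1% |
| None | 15% | 19.2% → 2.6% | 28.7% → 6.8% | 39.4% → 11.7% |
| −15% (SD by definition) | 5% | 9.3% → 0.8% | 14.9% → 2.4% | 22.2% → 4.5% |
| −15% (SD by definition) | 10% | 37% → 8% | 50% → 18% | 62% → 28% |

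If all 30 patients were truly unchanged and had six readings each, the expected false MRs would be 0.0 → 0.0 (CV 5%), 30 × 0.088 = 2.6 → 0.3 (CV 10%) and 8.6 → 2.0 (CV 15%).

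**6. Sensitivity.**

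- If readings were 8-weekly, six cycles would give three. At CV 10% with no true change the one-value figure is again 5.3%. The next reading would then serve as the repeat, giving 0.6%.
- With error correlation 0.5 between successive readings (baseline included), CV 10%, no true change and six readings, the figures are 5.5% on one value and 0.8% with a repeat two cycles on. Both are lower, but the gap remains.

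**The case against.** The strongest reply is that little depends on this. The primary endpoint is the MTD, which rests on dose-limiting toxicities alone. Efficacy is secondary, untested and based on at most 30 patients. Section 11 plans only frequency tables of toxicity. If the categories are tabulated separately, the CR and PR lines are untouched. All of this stands, and it limits the point to the MR line and to any rate that includes it.

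The size rests on an assumed CV. With no true change at CV 5% the effect vanishes, and that belongs in the stated range. It returns at CV 5% for a patient with a true 15% fall.

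The number of readings is not settled either. Section 8 and footnote 13 say every cycle, while footnote 9 starts assessment after cycle 2. Fewer readings mean a smaller effect, as the three-reading column shows.

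Section 8 cites published response recommendations, which are not available here. Whether leaving MR unconfirmed departs from them cannot be judged. That does not alter the arithmetic.

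Three stronger inferences are tempting but unsupported:

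- **That the trial will overstate pomalidomide's activity.** No response rate counting MR is defined, and the true CV is unknown. The documents support only that the MR count can be inflated.
- **That MR is the only IgM-defined category left unconfirmed.** SD is too.
- **That temporary IgM falls after plasma exchange would be credited.** No passage mentions plasma exchange. New symptoms or signs of active disease already rule out MR, and hyperviscosity attributable to the disease is listed under PD.

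**Conclusion.** The point holds as a limited one. MR lacks the confirmation that the plan requires for CR, PR and IgM-based PD. Under best response over an open-ended course, one reading 25% to under 50% below baseline is enough to record it, provided there are no new symptoms or signs and no confirmed PR or CR. The error runs upward and grows with the number of readings.

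On the stated assumptions, with six readings and no true change, the chance of a false MR ranges from negligible (CV 5%) through about 9% (CV 10%) to about 29% (CV 15%). A repeat removes most of it. The range reflects an IgM variability that the documents do not give, so no single figure should be quoted as the bias. Dose escalation, the MTD, and the CR and PR counts are not affected. This is a worthwhile, inexpensive improvement to a secondary endpoint and not a threat to the trial's main purpose.

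**What to change.** - **Extend the confirmation rule.** In Section 8 and footnote 14, add MR to the existing requirement: the IgM reduction of 25% or more must be present again at a scheduled response assessment at least 6 weeks later, otherwise best response is SD. Wording it as 25% or more also places an unconfirmed single fall of 50% or more, which now has no category because MR stops below 50%. Keeping the 6-week interval avoids a second standard. Accepting the next cycle's value performs almost the same (1.2% against 1.1% at CV 10%, no true change, six readings).
- **Report unconfirmed MR on a separate line**, and state in Section 5.2.2 or 11 whether any response rate includes MR.
- **Reconcile the timing.** Section 8 and footnote 13 (each cycle) and footnote 9 (first assessment at completion of cycle 2) should agree.

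The cost is a few sentences. If labs are drawn every cycle as footnote 13 states, no extra visit or blood draw is needed. The downside is that a few patients who stop soon after a first 25% fall will be scored SD; the separate line keeps them visible.

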⁴Electrolytes, BUN, Creatinine, Calcium, Magnesium, Phosphorous, Albumin, Total Bilirubin (fractionated, if elevated), ALT, AST, Alkaline Phosphatase, Beta 2 microglobulin; A Thyroid Stimulating Hormone (TSH) level is to be drawn at Screening, and as clinically indicated. T3 and T4 levels may be assessed as clinically indicated. Cryocrit, Cold Agglutinin Titer and serum viscosity are to be drawn at screening; if abnormal on screening, they are to be repeated at treatment discontinuation (within 5 days prior to Day 1 of each cycle).

⁵Indicated for females of childbearing potential. A female of childbearing potential (FCBP) is a sexually mature female who: 1) has not undergone a hysterectomy or bilateral oophorectomy; or 2) has not been naturally postmenopausal for at least 24 consecutive months (i.e., has had menses at any time in the preceding 24 consecutive months).

⁶Pregnancy tests (either urine or serum β HCG) must occur 10 – 14 days prior, and again within 24 hours prior to initiation of pomalidomide. FCBP with regular or no menstruation must have a pregnancy test weekly for the first 4 weeks and then every 28 days while on therapy (including breaks in therapy); at discontinuation of pomalidomide and at Day 28 post the last dose of pomalidomide. Females with irregular menstruation must have a pregnancy test weekly for the first 4 weeks and then every 14 days while on therapy (including breaks in therapy), at discontinuation of pomalidomide and at Day 14 and Day 28 post the last dose of pomalidomide (see Appendix A: Risks of Fetal Exposure, Pregnancy Testing Guidelines and Acceptable Birth Control Methods).

⁷All patients must be counseled about pregnancy precautions, risks of fetal exposure and other risks. The counseling must be done on Day 1 of each cycle (or at a minimum of every 28 days) and at drug discontinuation. See Appendix A: Pomalidomide Risks of Fetal Exposure, Pregnancy Testing Guidelines and Acceptable Birth Control Methods and Appendix B: Pomalidomide Education and Counseling Guidance Document

⁸If these CT/MRI assessments show no adenopathy or hepatosplenomegaly at screening, they will only be repeated at discontinuation of study drug. These imaging studies should be performed within 7 days prior to Day 1 of each odd cycle.

⁹All PRs and CRs must be confirmed by repeat scans no less than 6 weeks after the criteria for response are first met. The first response assessment will take place at completion of cycle 2.

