11.2 Datasets to be analyzed

Data from all subjects who receive any study drug will be included in the determination of the maximum tolerated dose, unless they withdrew from the study before completing 1 cycle of therapy for reasons other than tolerability/toxicity.

Data from all subjects who receive any study drug will be included in the safety analyses. Subjects who enter the study but do not take any of the study drug(s), and have had this confirmed, will not be evaluated for safety.

Data from all subjects who received at least 1 cycles of therapy will be used in the analysis of drug efficacy.

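### Under Section 8's timing, stable disease can be assigned after one cycle but progression cannot be confirmed until after two, so best-response coding leans toward stable disease

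*Combined protocol and SAP*

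**What the plan says.** - **Definition (Section 8, item 4).** Stable disease is less than a 25% fall and less than a 25% "increase of serum monoclonal IgM concentration determined by protein electrophoresis, without progression of adenopathy/organomegaly, cytopenias or clinically significant symptoms caused by disease". No minimum duration, earliest time point or confirmation is attached.
- **Timing (Section 8).** "Response assessments will be performed after each cycle of pomalidomide has been administered". Section 2 footnote 13 matches this for the laboratory part: "Response assessment labs should be performed within 5 days prior to Day 1 of each cycle".
- **Timing (Section 2, footnote 9, on the CT/MRI row).** "The first response assessment will take place at completion of cycle 2".
- **Other categories (Section 8).** Complete and partial responses need a second assessment at least 6 weeks later. Because of IgM flare, progressive disease may not be confirmed before the post-Cycle 2 assessment has been reviewed. An IgM rise of 25% or more also needs a repeat measurement; clinical progression is a separate route to progressive disease.
- **Endpoint (Section 5.2.2).** "It will be assessed as the best response during each patient's course of therapy".
- **Who counts.** Section 5.2.2: "Patients will be considered evaluable if they have completed at least 1 cycle of therapy". Section 11.2: "Data from all subjects who received at least 1 cycles of therapy will be used in the analysis of drug efficacy".

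No rule states how stable disease followed by progression is coded. No progression-free survival or duration-of-stability endpoint is defined.

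**The concern.** The timing rules are one-sided. At the end of Cycle 1 a patient can be given stable disease, but confirmed progression is not yet available. Section 8 treats an early IgM rise as too unreliable to establish progression, yet lets the measurement at the same visit establish stability, in a disease that the protocol describes as low grade. Taking the best category over the course then keeps the earlier, more favourable label.

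Best response is the only efficacy endpoint, and the cohorts are small. A few patients coded stable on 28 days of observation would visibly change the reported split between stable and progressive disease. Because footnote 9 and Section 8 disagree on when response is first assessed, two readers could also code the same patient differently.

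**Working it through.** The plan states no figure that depends on this definition, so there is none to reproduce. The check sets the rules side by side and adds an illustration.

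**1. What can be coded, and when (Section 8 timing)**

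| Category | Earliest assignment | Confirmation |
|---|---|---|
| Complete or partial response | end of Cycle 1 | at least 6 weeks later |
| Stable disease | end of Cycle 1 | none |
| Progressive disease | after the Cycle 2 review | repeat measurement if by IgM |

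A patient who stops after one cycle is evaluable and can be coded stable, but cannot have confirmed progression.

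**2. Growth rates that fall in the gap**

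Inputs: the 25% threshold (Section 8) and 28-day cycles (Section 6.4.2). Assumption: constant proportional IgM growth *g* per cycle from Day 1.

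- Stable after Cycle 1: (1 + g) < 1.25.
- At the progression threshold after Cycle 2: (1 + g)² ≥ 1.25, so g ≥ √1.25 − 1 = 0.118.
- The window is therefore 11.8% to just under 25% per cycle.
- Doubling time = 28 × ln 2 / ln(1 + g), which is about 174 days at 11.8% and about 87 days at 25%.

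Example: at +15% per cycle, IgM is +15% after Cycle 1 and 1.15² − 1 = +32% after Cycle 2. If the second value is confirmed on repeat, and there was no clinical progression at Cycle 1, best response is stable disease.

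**3. Share of patients in the window**

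The documents give no IgM kinetics. The rows below assume no drug effect and normally distributed per-cycle growth. They ignore measurement error and the repeat measurement for progression. The share is P(0.118 ≤ g < 0.25). Twelve is the 6 patients needed to define the MTD (Section 11.1) plus the additional 6 (Section 6.4.2).

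| Mean growth (standard deviation) | Share in window | Of 12 patients | Already ≥ 25% at Cycle 1 |
|---|---|---|---|
| 2% (5%) | 2.5% | 0.3 | about 0% |
| 5% (8%) | 19% | 2.3 | 0.6% |
| 10% (10%) | 36% | 4.3 | 6.7% |
| 15% (12%) | 40% | 4.8 | 20% |

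**4. If footnote 9 governs instead**

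The first assessment is then at about day 56. Growth of 11.8% to just under 25% would be progression at that first assessment, once confirmed. The window for being stable at one assessment and progressing at the next moves to 1.25^(1/3) − 1 = 7.7% up to 11.8% per cycle, or doubling times of about 174 to 261 days. A different gap opens: a patient with one completed cycle is evaluable but has no scheduled response assessment, hence no category.

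**The case against.** **Cycle 1 timing is not settled.** A reader might infer that one-cycle stable disease is an established rule. It is not. Footnote 9 sits on the imaging row, but its sentence is not limited to scans. Scheduled imaging also starts only with Cycle 3 (footnotes 8 and 21), so the nodal part of the definition is not imaged after Cycle 1. This stands: the point is a conflict between two passages plus a missing coding rule.

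**Progression is not hidden.** Section 8 has each response documented in the data system, and Section 6.7 lists progression as a reason for ending treatment. It is lost only from the best-response table. That a later progression leaves stable disease as the best category is itself inferred from the term best response.

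**Progression as best response is not close to impossible.** Clinical progression excludes stable disease whatever the IgM. A rise of 25% or more at Cycle 1 that persists is also still progression.

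**No disease-control rate is inflated.** It is tempting to say that a proportion with stable disease or better is biased upward, but the protocol defines no such proportion.

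**The size depends on the assumption.** A reader might settle on 2 to 5 of 12 patients. Mean growth of 10% or 15% per cycle compounds over 13 cycles to about 3.5-fold or 6.2-fold in a year, which sits poorly with a low-grade disease; the 2% row gives 0.3 of 12. Section 8 also asks for an absolute 5 g/L rise when M protein is the only criterion. That sentence appears under progression from partial response and its reach is unclear. If it applied generally, a 25% rise from a baseline below 20 g/L would not be progression (0.25 × 20 = 5).

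**No document requires a minimum duration.** True, and the published response criteria that Section 8 cites cannot be consulted here. The point rests on the asymmetry inside Section 8 and its conflict with footnote 9.

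**Conclusion.** The point holds in limited form. Under Section 8's timing, stable disease has no earliest time point while progression does. With best response as the endpoint and one-cycle evaluability, a patient with IgM within 25% of baseline and no clinical progression after Cycle 1, then confirmed progression from the Cycle 2 assessment, is coded stable. The bias runs one way, toward stable disease.

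Its reach is the split between stable and progressive disease in a descriptive secondary endpoint. Complete, partial and minor response counts, the MTD and the sample size are unaffected. The size cannot be fixed from the documents: about 2.5% to about 40% of patients under the growth assumptions shown, all with no drug effect and without the progression confirmation step. The contradiction between footnote 9 and Section 8 needs resolving whatever the growth rate.

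**What to change.** Reconcile Section 2 footnote 9 with Section 8 on when response is first assessed, and add a coding rule for the best-response table to Section 8:

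> Stable disease as best response requires the stable-disease criteria to be met at the end-of-Cycle-2 assessment (labs in the footnote 13 window before Cycle 3 Day 1) or later. A patient with no earlier complete, partial or minor response who has progressive disease at that assessment (IgM rise confirmed as Section 8 requires), or clinical progression before it, is coded progressive disease. Any other patient without an assessment at or after the end of Cycle 2 is coded not evaluable and kept in the denominator.

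Two details matter. Tying the rule to the footnote 13 window avoids a flat 8-week bar: labs drawn 1 to 5 days before an on-schedule Cycle 3 fall 51 to 55 days after the first dose and would miss 56 days. Coding early clinical progression as progressive disease keeps those patients from disappearing into the not-evaluable group. Since Section 8 delays confirmation of progression because of IgM flare, the text should say that this clause governs table coding only and does not alter when treatment stops.

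Cost: a few patients move from stable to progressive disease or not evaluable. No new visits or tests are needed. The rule does not remove every such case: growth of 7.7% to 11.8% per cycle would still be stable at Cycle 2 and reach the threshold at Cycle 3, but after about 8 weeks of observation instead of 4.
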